1.3.2.2. Selection of Dose Levels

The nonclinical safety profile of PF-06882961 was adequately characterized to support progression into human clinical studies encompassing dosing periods up to 4 weeks in duration (see [Section 1.2.3](#)).

The doses proposed for this study were determined considering all relevant information obtained from nonclinical safety studies along with preliminary safety, tolerability, and PK data observed in the ongoing study C3421001.

A starting dose of 15 mg PF-06882961 BID is planned. At this dose, the projected average concentration of PF-06882961 at steady-state is approximately 9-fold below the projected C_{eff} (see [Section 1.3.2.1](#)). Based on preliminary data from study C3421001 ([Section 1.2.4](#)), this dose is expected to have an acceptable safety and tolerability profile.

The dose range for this study was chosen in order to appropriately bracket the projected efficacious dose to cover the potential impact of uncertainty in projection of efficacious concentration or of unanticipated factors on drug exposure, while accommodating feasibility considerations including tablet burden. The highest planned dose will be identified as the dose deemed to be the maximum tolerated dose (MTD) upon repeated administration or a total daily dose of 1600 mg (800 mg BID), whichever is the most conservative. At steady state, a dose of 800 mg BID is projected to yield an average concentration approximately 6-fold above the projected C_{eff} (see [Section 1.3.2.2](#)) and is projected to yield C_{max} and AUC_{24} exposures approximately 16- and 11-fold below the defined human exposure limits ie, the NOAEL in a 4-week toxicology study in rats (see [Section 1.2.3](#) and [Section 3.2](#)).

Dose escalation to the NOAEL in the 4-week toxicology study in rats is proposed due to the fact that no adverse findings were noted at the highest dose administered in nonhuman primates and that nonadverse findings such as decreased food intake were reversible in the nonhuman primates and are monitorable in a clinical setting ([Section 1.2.3](#)). Predicted exposure levels and safety margins for a range of anticipated doses for this study are provided in [Table 5](#) below. All exposure-based safety margins were calculated using unbound concentrations. This table gives an overview of the potential dose levels however the increment of C_{max} and AUC_{24} between dose levels will be targeted to be approximately semi-logarithmic.

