9.7.2. Vital Sign Analysis

Supine blood pressures and pulse will be recorded at each assessment time indicated in the [Schedule of Activities](#). The average of any triplicate measurements will be calculated prior to analyzing the data.

The maximum decrease/increase in blood pressures and pulse rate from time-matched baseline (Day -1) over all measurements taken post-dose, will be determined for each subject.

No formal inferential statistics will be applied to the vital signs data.

Actual values and changes from time-matched baseline in supine systolic and diastolic and pulse rate will be summarized by treatment, time postdose and day.

The supine systolic and diastolic BP and pulse rate measurements obtained following the Day 1 dose will have their corresponding Day 1 predose value subtracted from them. These values will then be compared with their corresponding values on Day-1, ie, the change in the time-matched Day -1 value from the baseline measure on that day. The differences will be summarized (N, mean, 90% CI) for each dose and time point. In addition, for supine systolic and diastolic BP and pulse rate, the time matched baseline subtracted differences between each dose and placebo will be summarized (N, mean, 90% CI) for each dose, time postdose and day.

Maximum values and maximum changes from time-matched baseline for vital signs will also be summarized descriptively by treatment using categories as defined in the statistical analysis plan. Numbers and percentages of subjects meeting the categorical criteria will be provided and individual values listed in the CSR.

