2.1. Study Design

This is a randomized, double-blind (sponsor-open), parallel, placebo-controlled, multiple oral dose-escalating study of PF-06882961 in subjects with T2DM on a background of metformin monotherapy.

[figure not shown]
Subjects will receive oral doses of PF-06882961 or placebo in this study. A total of approximately 12 subjects (9 active and 3 placebo) will be enrolled in each cohort, for a total of approximately 60 (Cohorts 1-5) or up to approximately 96 (if including optional Cohorts 6-8) subjects randomized. The randomization ratio within a cohort will be 3:1 between PF-06882961 and placebo. The study will be conducted at approximately 2-5 clinical sites in the US.

Dose titration will be incorporated to enhance tolerability to PF-06882961. Doses and dose titration schemes in the escalation sequence may be modified or repeated as guided by emerging safety, and PK data. The size of the dose increment and titration rate may be reduced or increased as the study progresses dependent upon emerging PK, safety and tolerability data, but dose increments from one cohort to the succeeding cohort will not be greater than approximately semi-logarithmic. Doses and dosing durations for Cohort 5 and optional Cohorts 6-8 will be provided to investigators in writing prior to initiation of dosing in these cohorts.

Subjects will be admitted to the clinical research unit (CRU) on or before Day -2 and may be discharged at PI discretion following completion of all assessments on Day 30. A Follow-up visit and a Follow-up contact (may be a phone call) will occur 35-42 days and 56-63 days following the first dose of IP on Day 1, respectively. Subjects who discontinue prior to completion of the study may be replaced, at the discretion of the PI and Sponsor.

The formulations administered in this study will be PF-06882961 **CCI** tablets, or matching placebo. A Sample study design overview is shown in Figure 1, however, treatment sequences, actual doses, target exposures, formulation, fasting state, titration, and dose increments may be adjusted during the study based on emerging safety, tolerability, and PK data.

Figure 1. Study Design Overview

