8. STATISTICAL METHODOLOGY AND STATISTICAL ANALYSES

Unless otherwise specified for safety ([Section 8.4](#)) and other analyses ([Section 8.3](#)), the placebo groups will be pooled by frequency of dosing (QD and BID, if applicable), along with one overall pooled group. CCI [REDACTED]

[REDACTED]

In this section (excluding PK analyses), ‘treatment’ refers to the randomized treatment labels that will be provided from GRAABS or the programming plan (along with placebo as above where relevant). Otherwise, ‘steady-state dose’ refers to the dose that subjects received during the Day 15 to Day 28 period (only applicable to cohorts that had 2 weeks titration and a BID regimen as per Cohorts 1-5). In the case where subjects do not complete this period and/or have multiple doses during this period, the dose most received during this period will be used for analyses. An additional listing of the treatment and steady-state dose for applicable subjects will be produced (including placebo subjects from the same cohorts).

As it is unknown to what extent subjects will be unable to reach the dose targeted as per the randomized treatment, based on emerging data additional tables and/or figures may need to be produced to aid in the interpretation of the safety and tolerability of PF-06882961. For example this could include, but is not limited to, producing AE tables restricted to events occurring during Day 15 to Day 28 only. If changes are required to currently specified tables and/or figures and additional outputs are required, this would be addressed with a SAP amendment prior to database closure.

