8.4.7. Vital Signs Data

Absolute values and change from time-matched baseline in supine systolic and diastolic blood pressure and pulse rate will be summarized by treatment, time post-dose and day, according to sponsor reporting standards. Tables will be paged by parameter. Baseline is as defined in [Section 6.2.3](#).

Mean change from time-matched baseline for supine systolic and diastolic blood pressure and pulse rate will be plotted against time post-dose and day. On each plot there will be 1 line for each treatment. Data from all cohorts will be plotted on the same figure using a single line for the placebo group(s). Corresponding individual plots of change from time-matched baseline will also be produced for each treatment.

Maximum absolute values and change from time-matched baseline for vital signs will also be summarized descriptively by treatment using categories as defined in [Appendix 1](#). Numbers and percentages of subjects meeting the categorical criteria will be provided. All planned and unplanned post-dose timepoints will be counted in these categorical summaries. All values meeting the criteria of potential clinical concern will be listed.

The time-matched double differences in vital signs obtained following the Day 1 treatment, as defined in [Section 6.2.3](#), will be summarized (N, mean, 90% confidence interval) for each treatment and time point. In addition, the time-matched double differences between each treatment and placebo will be summarized (N, mean, 90% confidence interval) for each treatment, time post-dose and day.

Mean time-matched double differences in vital signs will be plotted against time post-dose for Days 1, 14, 21 and 28 separately. On each plot there will be 1 line for each treatment and a single line for the placebo group(s). Corresponding individual plots of time-matched

double differences will also be produced for each treatment. The mean plots will similarly be produced for the time-matched double differences between each treatment and placebo.

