8.4.8. ECG Data

Absolute values and change from time-matched baseline in QT interval, heart rate, QTcF interval, PR interval and QRS interval will be summarized by treatment and time postdose using sponsor reporting standards. Tables will be paged by parameter. Baseline is as defined in [Section 6.2.4](#).

Mean change from time-matched baseline in ECG parameters will be plotted against day (for Days 1, 14, 21 and 28). On each plot there will be 1 line for each treatment and a single line for the placebo group(s). Corresponding individual plots of change from time-matched baseline will also be produced for each treatment.

Maximum increase from time-matched baseline (Day 1 to Day 14, Day 15 to Day 28 and overall, produced separately) for QTcF and heart rate will be summarized by treatment, according to sponsor reporting standards.

ECG endpoints and change from time-matched baseline (QTcF, PR and QRS) will also be summarized descriptively by treatment using categories as defined in [Appendix 1](#) (for QTc these correspond to the Pfizer Guidance as referenced in [Section 9](#)). Numbers and percentages of subjects meeting the categorical criteria will be provided. All planned and unplanned post-dose time-points will be counted in these categorical summaries. All values meeting the criteria of potential clinical concern will be listed.

Listings of subjects with any single post-dose value >500 msec will also be produced for QTcF.

The time-matched double differences in QT, QTcF, PR, QRS intervals and heart rate measures obtained following the Day 1 treatment, as defined in [Section 6.2.4](#), will be summarized (N, mean, 90% confidence interval) for each treatment and time point. In addition, the differences between each treatment and placebo will be summarized (N, mean, 90% confidence interval) for each treatment, time postdose and day.

Mean time-matched double differences in ECG parameters will be plotted against time postdose for Days 1, 14, 21 and 28 separately. On each plot there will be 1 line for each treatment and a single line for the placebo group(s). Corresponding individual plots of time-matched double differences will also be produced for each treatment. The mean plots will similarly be produced for the time-matched double differences between each treatment and placebo.

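### Day 1 vital-sign and ECG results are grouped by randomized label, so under the sample titration scheme one 15 mg BID dose is reported as four groups of 9 and never estimated from all 36 subjects

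*SAP*

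**What the plan says.** **Grouping.** SAP 8 states that, outside PK, treatment "refers to the randomized treatment labels that will be provided from GRAABS or the programming plan". The only dose-based alternative defined there, the steady-state dose, "refers to the dose that subjects received during the Day 15 to Day 28 period", so it cannot apply to Day 1.

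**Day 1 outputs.** SAP 8.4.7 says that the Day 1 double differences in blood pressure and pulse "will be summarized (N, mean, 90% confidence interval) for each treatment and time point". SAP 8.4.8 does the same for the QT, QTcF, PR, QRS and heart-rate values "obtained following the Day 1 treatment". Both sections add differences from placebo, with 90% CIs, by treatment, time and day. Both also plan a separate Day 1 mean plot with one line per treatment.

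**Doses.** Protocol 1.3.2.2 says: "A starting dose of 15 mg PF-06882961 BID is planned". Table 6 shows 15 mg BID on Day 1 for each of Cohorts 1-4; Cohorts 2-4 titrate upward from Day 2. Protocol 1.3.2.3 calls the scheme illustrative, and Cohort 5 and the optional cohorts are still to be determined.

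**Protocol analysis.** For the Day 1 vital-sign double differences, protocol 9.7.2 says: "The differences will be summarized (N, mean, 90% CI) for each dose and time point". For ECG changes, protocol 9.7.1 groups by treatment and time.

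**Size.** SAP 2.1: "A total of approximately 12 subjects (9 active and 3 placebo) will be enrolled in each cohort".

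**The concern.** Vital signs and ECGs are among the primary endpoints. On Day 1 no subject has had earlier study drug, and the double difference removes both the predose level and the Day -1 time course, so Day 1 is a clean look at the acute effect of the first dose. What distinguishes Cohorts 2, 3 and 4 from Cohort 1 at that point is a dose they have not yet received.

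Grouping by label has two costs. The four groups will differ by chance, and side-by-side columns or lines invite a reader to look for a trend where a dose effect is impossible. In addition, the quantity that Day 1 can estimate, 15 mg BID against placebo, is not planned to be estimated from all the subjects who contribute to it.

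**Working it through.** **Stated sizes.** 5 × 12 = 60 and 8 × 12 = 96 reproduce the planned totals. The 3:1 ratio splits 12 into 9 active and 3 placebo. The plan states no power or precision figure to reproduce.

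**Inputs.**
- Active subjects on 15 mg BID on Day 1 under Table 6: 4 × 9 = 36, reported as four groups of 9.
- Pooled placebo: SAP 8 pools placebo by dosing frequency and overall, and 8.4.7 and 8.4.8 do not say otherwise. That gives 12 subjects (Cohorts 1-4), 15 (Cohorts 1-5), or up to 24 (all eight cohorts).
- The documents give no SD, so results are in SD units, assuming a common SD.

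**Active mean.** 90% half-width = t(0.95, n−1) / √n.
- n = 9: 1.860 / 3 = 0.620 SD.
- n = 36: 1.690 / 6 = 0.282 SD.
- Ratio 0.282 / 0.620 = 0.454, about 55% narrower when pooled. In variance terms each group of 9 carries 9/36 of the information, so 75% is given up.

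**Active minus pooled placebo.** 90% half-width = t(0.95, n+m−2) × √(1/n + 1/m).

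| Placebo m | Half-width, n = 9 | Half-width, n = 36 | Narrower by | Information given up by splitting |
|---|---|---|---|---|
| 12 | 1.729 × 0.441 = 0.763 | 1.679 × 0.333 = 0.560 | 27% | 43% |
| 15 | 1.717 × 0.422 = 0.724 | 1.677 × 0.307 = 0.515 | 29% | 47% |
| 24 | 1.696 × 0.391 = 0.663 | 1.672 × 0.264 = 0.441 | 34% | 55% |

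The last column is 1 − (1/36 + 1/m) / (1/9 + 1/m). The gain is smaller than for the active mean because the placebo variance does not change.

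**Chance spread.** With no true difference, four independent means of 9 are expected to span about 0.69 SD from lowest to highest. If the SD of pulse change were 8 bpm (an assumption; range 6 to 10), that is about 5.5 bpm (4.1 to 6.9).

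**The case against.** Several points on the other side stand.

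- **Table 6 is only a sample.** Doses and titration may change, so the figure of 36 is conditional. Grouping by the dose actually received removes the dependence.
- **The column headings are not shown.** A reader might infer that identical doses will be headed with target doses up to 300 mg BID, creating a false dose-response. The documents do not support that: the labels come from a source outside them and may spell out the titration steps. That would make misreading less likely, but it would not recover the precision.
- **ECG matches the protocol.** A reader might infer that SAP 8.4.8 also breaks from the protocol. It does not, since 9.7.1 already groups by treatment and 9.7.2 covers vital signs only. Even for vital signs, 9.7.2 uses both dose and treatment, does not spell out pooling across cohorts, and protocol section 9 lets the SAP modify the outline.
- **The stakes are modest.** SAP 4.1 and 4.2 set no hypotheses or decision rules, and SAP 8.4 plans no formal safety analysis. The starting dose is projected to be about 9-fold below the efficacious concentration. N and the CI are printed, so imprecision is visible.
- **Part is covered.** SAP 8.4.8 plots QTcF double differences against concentration regardless of label, but nothing similar is described for blood pressure or pulse. SAP 8 allows extra outputs by amendment, but the case it foresees is subjects who do not reach their target dose.

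What remains is that no planned Day 1 summary groups these data by dose taken.

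**Conclusion.** The point holds as a cheap improvement to descriptive outputs on primary safety endpoints. Under Table 6, the SAP reports one Day 1 dose as four groups of 9, and differences between those groups cannot be dose effects. For vital signs the SAP also departs from the dose-based grouping in protocol 9.7.2; for ECG the case rests on logic alone.

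A reader might infer that splitting loses most of the precision of the placebo contrasts. It does not. Placebo is already pooled, so with 12-15 placebo subjects the split gives up 43-47% of the information, and pooling narrows the 90% CI by 27-29%. The loss passes half (55%) only if all eight cohorts supply 24 placebo subjects. The larger figures, 55% narrower and 75% of the information, belong to the within-group active mean.

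A reader might also infer that by-label contrasts should wait until Day 15. That would discard useful output: Day 14 is a full serial ECG and vital-sign day in protocol Table 2, and under Table 6 Cohorts 1-4 are all scheduled at target (or individual MTD) by then, Cohort 4 from Day 7.

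The figures assume that Cohorts 1-4 start as in Table 6, 9 active subjects per cohort, a common SD, and no cohort or site effect on Day 1.

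**What to change.** Keep every by-label table and plot, including Day 14. In SAP 8.4.7 and 8.4.8:

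1. Add a Day 1 summary of the double differences, and a Day 1 contrast with pooled placebo (N, mean, 90% CI, by time point), grouped by the dose actually received on Day 1 and pooling all cohorts given that dose and regimen.
2. Footnote the Day 1 by-label columns to say that cohorts sharing a Day 1 dose do not form a dose comparison.

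The cost is one derived grouping variable, a sentence in each section and a few extra tables. Pooling active subjects assumes no cohort effect on Day 1, an assumption the SAP already makes when it pools placebo across cohorts; the retained by-label columns let a reader check it. Data collection, error rates and sample size do not change.

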3. STUDY DESIGN

3.1. Study Overview

This is a randomized, double-blind (sponsor-open), parallel, placebo-controlled, multiple oral dose-escalating study of PF-06882961 in subjects with T2DM on a background of metformin monotherapy.

Subjects will receive oral doses of PF-06882961 or placebo in this study. A total of approximately 12 subjects (9 active and 3 placebo) will be enrolled in each cohort, for a total of approximately 60 (Cohorts 1-5) or up to approximately 96 (if including optional Cohorts 6-8) subjects randomized. As a result, the maximum number of cohorts in the study will not exceed 8, corresponding to a maximum of 96 completed subjects. The randomization ratio within a cohort will be 3:1 between PF-06882961 and placebo. The study will be conducted at approximately 2-5 clinical sites in the US. Attempts will be made to equally balance the enrollment of subjects to active and placebo across sites within each cohort. It is not necessary for every site to participate in every cohort. For each cohort, an attempt will be made to have at least 1 subject randomized to placebo per site, which will be facilitated through block randomization.

Dose titration will be incorporated to enhance tolerability to PF-06882961 (see [Section 1.3.2.3](#)). Doses and dose titration schemes in the escalation sequence may be modified or repeated as guided by emerging safety, and PK data. The size of the dose increment and titration rate may be reduced or increased as the study progresses dependent

[figure not shown]
upon emerging PK, safety and tolerability data, but dose increments from one cohort to the succeeding cohort will not be greater than approximately semi-logarithmic. Doses and dosing durations for Cohort 5 and optional Cohorts 6-8 will be provided to investigators in writing prior to initiation of dosing in these cohorts. Predicted steady state exposures for all cohorts will also not exceed the proposed PK stopping limits (see [Section 1.3.2.3](#) and [Section 3.2](#)).

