6.2.3. Vital Signs

Single supine blood pressure and pulse rate measurements will be taken at screening, Day 30, Follow-up and at early termination (if applicable). Triplicate supine measurements will be taken at all other times as detailed in the Schedule of Activities given in the protocol. The average of the triplicate measurements will be calculated prior to analyzing the data. Baseline will be defined as the time-matched value from the average of the triplicate recordings on Day -1.

The time-matched double difference in supine blood pressures and pulse rate measurements is calculated in the following steps: (1) subtract predose value on Day 1 from all postdose values; (2) subtract the value at 0 hours on Day -1 from all other values on Day -1; (3) take the difference between the adjusted postdose value in (1) and its time-matched value in (2).

The maximum decrease and increase from time-matched baseline over all measurements taken postdose will be calculated for supine systolic and diastolic blood pressures. The maximum increase from baseline will be calculated by first subtracting the time-matched baseline value from each postdose measurement to give the change from baseline. The maximum of these values over the respective period will then be selected, except in the case where a subject does not show an increase. In such an instance, the minimum decrease should be taken. Similarly, the maximum decrease from baseline will be determined by selecting the minimum value of the change from baseline. In cases where a subject does not show a decrease, the minimum increase should be taken.

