8.1.6. Analysis of Covariance

The ANCOVA model will include the change from baseline of the relevant endpoint as specified in [Section 8.4.9](#) as the dependent variable and will include treatment as a fixed effect and baseline as a covariate.

Missing values will not be imputed.

The Least Squares Means (LSMeans) together with 90% confidence intervals and standard errors will be obtained for each treatment. Differences in LSMeans between each treatment and placebo, together with 90% confidence intervals and standard errors, will also be obtained.

Standard SAS output will be provided to support the main statistical summary table for the models.

Example SAS code is provided in [Appendix 3](#).

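### Placebo contrasts for blood pressure, pulse and ECG are unadjusted differences of baseline-subtracted values; they are unbiased over randomizations but less precise than a baseline ANCOVA the SAP already contains

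*SAP*

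**What the plan says.** Protocol section 2 puts vital signs and 12-lead ECGs in the primary endpoint. Group sizes come from Protocol 3.1: "A total of approximately 12 subjects (9 active and 3 placebo) will be enrolled in each cohort". SAP section 8 sets the comparator: "the placebo groups will be pooled by frequency of dosing (QD and BID, if applicable), along with one overall pooled group".

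For vital signs, SAP 6.2.3 says "Baseline will be defined as the time-matched value from the average of the triplicate recordings on Day -1". It then builds a double difference in three subtractions: post-dose minus Day 1 predose, Day -1 at the same time minus Day -1 at 0H, and the first result minus the second. SAP 6.2.4 does the same for ECG.

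The placebo contrasts use these quantities. SAP 8.4.7 says "the time-matched double differences between each treatment and placebo will be summarized (N, mean, 90% confidence interval) for each treatment, time post-dose and day". SAP 8.4.8 says "the differences between each treatment and placebo will be summarized (N, mean, 90% confidence interval) for each treatment, time postdose and day"; that sentence does not repeat the term double difference, but the plots described after it do. Neither section names a model or a covariate.

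Protocol 9.7.2 describes the vital-sign contrast differently: "the time matched baseline subtracted differences between each dose and placebo will be summarized (N, mean, 90% CI) for each dose, time postdose and day". That is a single time-matched subtraction.

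The SAP does contain a baseline-adjusted model. The ANCOVA of SAP 8.1.6 "will include treatment as a fixed effect and baseline as a covariate". It points to SAP 8.4.9, where it is applied to HbA1c.

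**The concern.** Subtracting a baseline is not the same as adjusting for it. A change score fixes the baseline coefficient at 1, whereas the data support a coefficient of about r. With about 9 subjects on a dose, some Day -1 difference from placebo is to be expected, and the over-correction falls in that dose's column.

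The double difference adds a second cost. It subtracts three noisy values instead of one, and on Days 14, 21 and 28 one of them is a Day 1 predose reading taken weeks before.

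Precision matters for these measures. Protocol 1.3.1 justifies triplicate readings by the wish to reduce variability in heart rate and blood pressure, and Protocol 1.2.3 reports nonclinical effects on blood pressure, heart rate and QTc. The planned contrast gives back part of what the triplicates gain, while HbA1c, which the primary endpoint does not name, gets the more efficient analysis.

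**Working it through.** **Figures in the plan.** 9 + 3 = 12 per cohort; 5 × 12 = 60 and 8 × 12 = 96, as stated. Pooled placebo is therefore about 5 × 3 = 15, or up to 8 × 3 = 24.

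**Assumptions.** The documents give no SD and no correlation. I assume a common SD s, the same correlation r between any two readings of a subject, and no reproducible individual diurnal pattern. I range r from 0.3 to 0.9. The SAP does not say how the 90% CI is computed; I assume a two-sample t interval. The double-difference algebra is for nominal times after 0H.

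**Size of a chance imbalance.** The SE of a Day -1 mean difference is s × sqrt(1/9 + 1/15) = 0.42 s, or s × sqrt(1/9 + 1/24) = 0.39 s with 24 placebo subjects.

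**Carry-over.** Let Y be the post-dose reading, P the Day 1 predose reading, B the Day -1 reading at the same time and B0 the Day -1 reading at 0H, with s = 1.

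- Single change Y − B: covariance with B is r − 1, so the slope on B is −(1−r).
- Double difference Y − P − B + B0: covariance with B is r − r − 1 + r, so the slope is again −(1−r).
- Double difference on the Day -1 time course B − B0: covariance −2(1−r), variance 2(1−r), so the slope is −1. This imbalance carries over one for one.

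**Precision.** Variances are per subject in units of s². Half-widths are in units of s, using t(0.95, 22 df) = 1.717 and the factor 0.4216.

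| r | 0.3 | 0.5 | 0.7 | 0.9 |
|---|---|---|---|---|
| Variance, single change 2(1−r) | 1.40 | 1.00 | 0.60 | 0.20 |
| Variance, double difference 4(1−r) | 2.80 | 2.00 | 1.20 | 0.40 |
| Variance, ANCOVA 1−r² | 0.91 | 0.75 | 0.51 | 0.19 |
| SE ratio, ANCOVA / single change, sqrt((1+r)/2) | 0.81 | 0.87 | 0.92 | 0.97 |
| SE ratio, ANCOVA / double difference, sqrt((1+r)/4) | 0.57 | 0.61 | 0.65 | 0.69 |
| 90% half-width, single change | 0.86 | 0.72 | 0.56 | 0.32 |
| 90% half-width, double difference | 1.21 | 1.02 | 0.79 | 0.46 |
| 90% half-width, ANCOVA | 0.69 | 0.63 | 0.52 | 0.32 |

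**Simulation.** I used 20,000 trials of 9 versus 15 at each r. All three contrasts averaged 0.00. Slopes on the time-matched Day -1 imbalance were about −0.70, −0.50, −0.30 and −0.10 for both subtraction methods and 0.00 for ANCOVA. The slope of the double difference on the Day -1 time course was −1.00. Estimating the ANCOVA slope from these 24 subjects alone costs a little: simulated SE ratios were 0.83, 0.89, 0.94 and 1.00 against the single change, and 0.58, 0.63, 0.67 and 0.71 against the double difference. Fitting all arms together should recover most of that.

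**In mmHg, assuming a systolic SD of 10 to 15, 9 versus 15.** A one-SE imbalance in the time-matched value is 4.2 to 6.3. Multiplied by (1−r), it shifts the contrast by 2.1 to 3.2 at r = 0.5, 1.3 to 1.9 at r = 0.7 and 0.4 to 0.6 at r = 0.9. A one-SE imbalance in the Day -1 time course is 0.42 s × sqrt(2(1−r)), and it shifts the double difference by its full size: 4.2 to 6.3, 3.3 to 4.9 and 1.9 to 2.8.

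**The case against.** A reader might infer that baseline imbalance passes whole into the safety estimates, or that the contrasts are biased. Neither follows. Subtraction removes the stable between-subject part. What is left of the time-matched imbalance is the (1−r) share with its sign reversed, and over randomizations it averages to zero. A valid interval already covers that variation: at r = 0.5 and SD 10 mmHg, the 2.1 mmHg shift sits inside a double-difference half-width of 10.2 mmHg.

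A reader might also infer that dose decisions rest on these numbers. They do not. Both documents call the safety analysis descriptive, SAP section 4 has no hypotheses or decision rules, and Protocol 3.2 bases escalation on clinically significant abnormalities, adverse events, PK limits and judgement. That limits the consequence. It does not remove the case, because the plan still promises placebo-contrast CIs for these measures, and the descriptive label did not prevent an ANCOVA for HbA1c in the same safety section.

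Three further points stand in part.

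- Averaged triplicates in confined, supine subjects may give a high r, and at r = 0.9 the gain over a single change is negligible. Stronger within-day correlation or reproducible diurnal patterns would also shrink the double-difference penalty.
- Eight parameters at about 23 times on the four intensive days make roughly 180 fits. That is a routine loop, but it adds tables.
- SAP 6.6 refers covariate details to 8.1.3 and 8.1.4, which are blacked out. The statement that only HbA1c is adjusted therefore holds for the visible safety text. SAP 8.4.7 and 8.4.8 are readable and cite no such model.

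**Conclusion.** The point holds as one about precision and conditional error. Under equal SDs and equal correlations, the planned double difference has 2.1 to 3.1 times the variance of a baseline ANCOVA; a single change score has 1.05 to 1.54 times. Either way, (1−r) of a chance imbalance in the time-matched Day -1 value shows up, reversed, in one dose column. The mmHg figures rest on an assumed SD and r and should be recalculated once blinded Day -1 data give real values. I have no figures for QTcF, PR or QRS; the ratios apply to them only if the same correlation assumptions hold.

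Separately, the SAP and Protocol 9.7.2 define the vital-sign placebo contrast differently. On these assumptions the choice between them doubles the variance.

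This is a recommended change. It does not threaten the validity of the study.

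**What to change.** In SAP 8.4.7 and 8.4.8, take the treatment-minus-placebo difference and 90% CI for each parameter, day and nominal time from the SAP 8.1.6 ANCOVA. Use change from the time-matched Day -1 value as response, treatment as fixed effect and the time-matched Day -1 value as covariate, with all arms in one model.

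Fit by REML. The ANCOVA code in SAP Appendix 3 uses method = ml and must be changed. With 60 subjects and 7 mean parameters (five active arms, pooled placebo, one slope), ML multiplies the SEs by sqrt(53/60) = 0.94, about 6% too small.

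Keep the raw means and double differences as descriptive tables. State which contrast is meant for vital signs so that the SAP and Protocol 9.7.2 agree.

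The cost is SAP wording, a small program edit and more tables; no new data are needed. The analysis remains estimation only. ANCOVA will not remove cohort differences that arise because pooled placebo subjects come partly from other cohorts.
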